3.8 Study variables

3.8.1 Independent Variables

Demographics

- . Age
- . Sex
- . Weight

Clinical

- . Pre-operative Hemoglobin

Fracture

- . Duration of Injury
- . Fracture Pattern (AO / OTA)

Surgery

- . General Anaesthesia
- . Regional Anaesthesia
- . Antegrade Nailing Technique

- . Retrograde Nailing Technique
- . Duration of Surgery

3.8.2 Outcome Variables

- . Primary Outcome: Perioperative blood loss –Will be represented as difference in the 2 hour pre-operative and 72 hour post-operative hemoglobin concentration in g/dl.
- . Secondary Outcome: Blood Transfusion – will be represented as the number of blood units. 450mls of whole blood will equate to 1 unit of whole blood. 200mls of packed cells will equate to 1 unit of whole blood.
- . Secondary Outcome: Safety – Will be described as adverse events secondary to administration of Tranexemic Acid observed in patients in the study during the perioperative period.
 - Anaphylaxis
 - Dizziness
 - Hypotension
 - Nausea and Vomiting
 - Diarrhoea
 - Thrombo -embolic Events
 - Others.....

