1.4 Research Hypothesis

Intravenous Tranexemic acid given preoperatively at 15mg/kg before open femoral shaft fracture intramedullary nailing will reduce average perioperative blood loss of 3.31 g/dl and perioperative transfusion rates by 30%.

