1.6.2.2 Secondary Objectives

1. To determine effectiveness of pre-operative intravenous Tranexemic acid 15mg/kg on reduction of transfusion rates in patients undergoing open intramedullary nail fixation of femoral shaft fractures in Mulago National Referral Hospital.
2. To determine the safety of pre-operative intravenous Tranexemic acid 15mg/kg in patients undergoing open intramedullary nail fixation of femoral shaft fractures in Mulago National Referral Hospital.

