the placebo was 2.7122 ± 2.70 , P value 0.000) a difference of 86.6% Results showed preoperative TXA caused a highly significant reduction in the blood loss in the first 24 hours in patients undergoing surgeries for hip and femoral fractures as well it caused a significant reduction in postoperative anemia and need for transfusion among these patients. In this study out of 45 patients, 18 patients (40%) who fell in the placebo group required blood transfusion and while 7 patients out of 45 (15%) in the study group needed a transfusion ($P=0.01$) a 25% difference in transfusion rates. This study recommended further investigation to determine the effectiveness of TXA in these surgeries.(33)

In Iran, double blinded randomized controlled clinical trial on role of preoperative TXA 15mg/kg versus placebo in intramedullary nailing of proximal femoral fracture shaft was done. With total of 40 patients, each study group was allocated 20 patients. Hemoglobin concentration was used to estimate blood loss, hemoglobin level was measured four hours before and after the surgeries. Blood transfusions observed and integrated into the blood estimation formula. Results showed No significant difference was observed between the groups in drain blood volume four hours after surgery. Mean fall in hemoglobin concentration in placebo group was higher than the TXA group, however, the difference was not statistically significant. ($P= 0.570$) A difference in transfusion rate between the placebo group (30%) and TXA group (5.6%) was also not statistically significant ($P=0.06$) a difference of 25%. Surgeon satisfaction level was also observed and noted to higher in the TXA group (94.4%) compared to the placebo group (80%), however the difference was not statistically significant. The study concluded that intravenous TXA before skin incision in patient undergoing proximal femoral shaft fractures surgery, may reduce intraoperative blood loss and hemoglobin fall however without significant reduction in postoperative anemia. This study recommended further investigations.(34)

CHAPTER THREE

METHODOLOGY

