3.12 Statistical analysis

Data will then be exported into a SPSS version 19 system which will be used for analysis. We will summarise the study population. We will use descriptive statistics such as means (standard deviations) or median and interquartile range (IQR) for continuous variables and proportions for categorized variables. We will also conduct appropriate statistical tests such as chi square or Fischer's test for categorical variables and a one sample independent T-test or wilcoxon sum rank test for continuous variables.

Objective 1: *To determine the effectiveness of pre-operative intravenous Tranexemic acid 15mg/kg on reduction of perioperative blood loss as estimated by difference in 72 hour postoperative and 2 hour preoperative Hemoglobin concentration in patients undergoing open intramedullary nailfixation offemoral shaftfractures in Mulago National Referral Hospital.*

We will assess for the hypothesis that TXA reduces perioperative blood loss by at least 30% using one sample independent T-test

Objective 2: *To determine effectiveness of pre-operative intravenous Tranexemic acid 15mg/kg on reduction of transfusion rates by 30% inpatients undergoing open intramedullary nail fixation offemoral shaftfractures in Mulago National Referral Hospital.*

We will conduct univariate analysis and adjust for effect modification and confounding.

Objective 3: *To determine the safety of pre-operative intravenous Tranexemic acid 15mg/kg in patients undergoing open intramedullary nailfixation offemoral shaftfractures in Mulago National Referral Hospital.*

We will assess for safety using descriptive statistics showing proportions of adverse events in the study group.

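### The transfusion objective is about the transfusion rate, but section 3.8.2 defines the outcome as a number of blood units, so the outcome as defined does not answer the objective

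*Combined protocol and SAP*

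**What the plan says.** **The question is put as a rate.** The hypothesis in section 1.4 is that treatment will reduce "perioperative transfusion rates by 30" per cent. Secondary objective 1 in section 1.6.2.2 concerns the effect "on reduction of transfusion rates in patients undergoing open intramedullary nail fixation". Section 3.12 restates this as Objective 2, with the target "on reduction of transfusion rates by 30" per cent. The abstract also lists transfusion rates among the things to be measured.

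**The outcome is defined as a count.** Section 3.8.2 is the only operational definition. There, transfusion "will be represented as the number of blood units", followed by a conversion from millilitres of whole blood or packed cells to units.

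**The analysis text does not settle it.** For Objective 2, section 3.12 says: "We will conduct univariate analysis and adjust for effect modification and confounding". It names no form of endpoint, no test and no reference value. The protocol nowhere defines transfusion rate.

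**The concern.** A rate in the sense of patients transfused, and a number of units, are different endpoints. The first depends only on whether a patient is transfused. The second also depends on how many units each transfused patient receives. Appendix III allows one unit at a time with reassessment before the next, so the two need not move together.

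An analyst who follows section 3.8.2 would produce a units figure and then have to draw a conclusion about rates. An analyst who follows section 1.4 would produce a proportion that the outcome section does not list. Treatment is open label and no analysis rule picks between the two, so the choice could be made after the results are known.

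**Working it through.** **1. What the protocol means by a rate.** The literature review gives:

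| Source in the protocol | Control or placebo | Tranexamic acid |
|---|---|---|
| Hip arthroplasty (2.3.2) | 26% | 17% |
| 90-patient hip and femoral study (2.3.3) | 18/45 = 40% | 7/45 = 15.6% (printed as 15%) |
| 40-patient proximal femoral nailing trial (2.3.3) | 30% | 5.6% |

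The 90-patient study is explicit about its denominator: "18 patients (40%) who fell in the placebo group required blood transfusion". The other two are percentages labelled as transfusion rates, which makes sense only as shares of patients. None is a number of units.

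**2. How the two endpoints relate.** Let p be the proportion transfused and m the mean units per transfused patient. Then units per patient U = p × m. Hypothetical example with 40 patients, 12 transfused in both cases:

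- Case A: p = 12/40 = 30%, m = 2.0, U = 12 × 2.0 / 40 = 0.60.
- Case B: p = 12/40 = 30%, m = 1.4, U = 12 × 1.4 / 40 = 0.42.
- Difference in U: (0.60 − 0.42)/0.60 = 30%. Difference in p: none.

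In whole units, Case B would be about 17 units against 24 in Case A, and 7/24 = 29%, so rounding does not alter the point. U cannot be turned back into p without the patient-level distribution.

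**3. What 30% could mean for a proportion.** Section 3.6.1 uses 30% as a relative reduction for blood loss (0.3 × 3.31 = 0.993 g/dl). Section 2.3.3 describes differences between transfusion rates in absolute terms (40% against 15%, called 25%). Applied to the cited control rates:

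| Reference rate | 30% relative reduction | 30 percentage points |
|---|---|---|
| 26% | 18.2% | not possible |
| 30% | 21% | 0% |
| 40% | 28% | 10% |

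**4. What the sample size can support.** The plan's calculation reproduces: 2 × (1.96 + 0.84)² × 1.56² / 0.993² = 38.7, rounded to 39, and 39/0.9 = 43.3, taken as 43. It concerns blood loss only. For a proportion, take n = 43 and an exact one-sided 0.025 binomial test. It rejects when the number transfused is at most r, the largest value with P(X ≤ r | p0) ≤ 0.025. Power for a 30% relative reduction is P(X ≤ r | 0.7 × p0):

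- p0 = 26%: r = 5, power 18%.
- p0 = 30%: r = 6, power 17%.
- p0 = 40%: r = 10, power 31%.
- p0 = 50%, 60%, 70%, 80% (assumed): power 44%, 56%, 77%, 91%.

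The documents give no local transfusion rate, so this is a range on assumptions.

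**The case against.** **Data capture is sound.** The data collection sheet in Appendix II records units for each patient, during and after surgery, so the proportion with at least one unit can be derived. The general paragraph of section 3.12 already provides proportions and tests for categorical variables. This stands: nothing is lost, and the fault lies in the definition and the analysis plan.

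**A quantity outcome has some basis.** Section 2.3.1 cites transfused volumes in spinal deformity surgery (544 against 812 mL, and 193 against 359 mL). The conceptual framework in 1.7 speaks only of less transfusion. This too stands, and is a reason to keep units as a supporting description. It does not make units a rate.

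**Stronger readings a reader might infer:**

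- *The two endpoints will give opposite answers.* The example above shows a fall against no change. Counts that reverse can be invented (in 43 patients, 17 to 12 transfused while units go from 17 to 18), but the documents give nothing to suggest that this is likely.
- *The 30% target could be met on one definition and missed on the other.* The single-arm plan gives no reference value for a rate or for units, so it cannot be shown to be met on either. This also weakens the worry about picking the favourable version, though it does not remove it.
- *The unit count will be mostly zeros.* No local transfusion rate is given, so this is unsupported, and the point does not need it.
- *A proportion could be tested against the cited rates.* Those come from other populations. Redefining the outcome does not make them a control group.

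**Conclusion.** The point holds as an internal inconsistency: the outcome in section 3.8.2 does not measure what sections 1.4, 1.6.2.2 and 3.12 set out to determine. The example shows that a 30% difference on one quantity can go with none on the other. That rests on hypothetical counts and shows only that divergence is possible. Reading the rate as a share of patients rests on the protocol's own usage in 2.3.2 and 2.3.3, since it gives no definition.

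This is a secondary outcome with no sample size of its own, and the repair is wording, but it should be made before analysis. Redefining the outcome does not by itself make a 30% reduction demonstrable. There is no comparator, and even against a fixed reference equal to the cited control rates of 26% to 40%, power would be only about 17% to 31% for a relative reduction. That favours estimation over a claim.

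**What to change.** - **Section 3.8.2:** define the secondary outcome as the proportion of patients receiving at least one unit (whole blood or packed cells) from start of surgery to 72 hours, which is the protocol's own perioperative window. Derive it from the recorded units and report it with an exact 95% CI. Keep units per patient as a supporting description.
- **Sections 1.4, 1.6.2.2 and 3.12:** use the same wording.
- **Section 3.12, Objective 2:** either name the reference transfusion rate and its source, and say whether 30% is relative or absolute; or present the proportion as an estimate and drop the claim of a 30% reduction. State that any comparison with the cited rates from other populations is descriptive only.

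The cost is wording. No new data, visits or patients are needed. The one item that may take effort is finding a defensible local reference rate, and the estimation option avoids it.

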NDA	- NATIONAL DRUG AUTHORITY
SOMREC	- SCHOOL OF MEDICINE RESEARCH AND ETHICS COMMITTEE
TXA	- TRANEXEMIC ACID
UBTS	- UGANDA BLOOD TRANSFUSION SERVICES

ABSTRACT

Background: Major Perioperative blood loss is one of the complications of open femoral shaft fracture intramedullary nailing surgery with average blood loss estimated at 1500mls. There is need for strategies to reduce on this blood loss. Antifibrinolytics such as tranexemic acid have been successfully used to reduce perioperative blood loss in other orthopaedic procedures.

However effectiveness of tranexemic acid use during open femoral shaft fracture intramedullary nailing surgery has not been studied in our setting.

Aim: To assess the effectiveness of intravenous tranexemic acid in reduction of perioperative blood loss, transfusion rates in patients undergoing open femoral shaft fracture intramedullary nailing surgery.

Methods: This will be an open label single arm study. Patients scheduled for open femoral shaft fracture intramedullary nail fixation surgery will receive preoperative tranexemic acid at 15mg/kg. Blood loss using difference between pre and post-operative hemoglobin, blood transfusion rates and adverse events in the peri operative period will be measured.

Utility: The results of this study will reveal effectiveness of tranexemic acid in reducing perioperative blood loss during open femoral shaft fracture surgery in this setting. This information will be useful in designing protocols for prevention of perioperative blood loss for femoral shaft fracture surgery.

OPERATIONAL DEFINITIONS

Peri-operative

- Period from start of surgery to 72 hours after the Surgery

ORIF

- Open intramedullary nailing of femoral shaft fractures.

CHAPTER ONE

INTRODUCTION

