3.7.4 Surgical Time

Time of skin incision and last skin suture will be documented to determine surgical time. It will be presented in minutes.

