3.7.7 Post-operative care

Patients in the immediate post-operative period will be monitored by the nurses on their primary wards noting vitals (Blood Pressure, Pulse Rate, Respiratory Rates and observe blood soiling of the surgical site dressing). Adequate analgesia will be given to the patients and mobilization in or out of bed will be instituted 12 hours following surgery with guidance of the physiotherapist as per patient tolerability.

Principal investigator together with the surgeons and residents on the primary wards will clinically review the patients daily as part of routine post-operative follow-up with emphasis on identifying and addressing post-operative complications such as thromboembolic phenomena e.g. DVT. Patients with features of thromboembolic phenomena or develop other Serious Adverse

Events will be investigated thoroughly with blood work up PT-INR, aPTT and Doppler Studies for the lower limbs. They will receive treatment as per guidance of qualified physician.

Serious Adverse Events (SAE) shall be reported within 24hours of occurrence to Department Of Orthopaedics, SOMREC, and National Drug Authority (NDA) using National SAE reporting tools.

Patients shall be followed up for a period of 2 weeks post operatively.

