APPENDIX II: Data Collection Sheet

Study Number.....

Date of Surgery

Study Arm A
 B

A. Patient information

1) Inpatient number 2) Age (yrs)

3) Sex: M F 4) Weight (kg)

B. Pre-operative Data

1) Duration of Injury (Days) 2) Fracture Pattern (AO / OTA)

 A B C

3) Preoperative Hemoglobin (g/dl) 4) Platelet Count

5) aPTT 6) PT-INR

C. Procedure Data

1) Type of Anaesthesia 2) Time : Start of Surgery

GA Regional

3) Time : End of Surgery 4) Duration of Surgery (hrs)

5) Nailing Approach 6) Whole Blood Units Transfused

Ante grade / Retrograde

7) Adverse Event/s Y N (Describe Event/s)

D. Postoperative Data

1) Whole Blood Units Transfused 2) 72hr Post-operative Hemoglobin (g/dl)

3) aPTT

4) PT-INR

Peri-operative Blood Loss (g/dl)

$$= \text{Pre-opHb} - (\text{Post-opHb} + \text{Blood Units})$$

$$= \dots - (\dots + \dots)$$

$$= \dots \text{ (g/dl)}$$

Intraoperative and Post-operative Adverse Events and complications

Pre / Intraoperative Period				Comments
DVT / TEE	Nausea Vomiting Diarhoea	Anaphylaxis Dermatitis	Hypotension	
Others				
Day 1				Comments
DVT / TEE	Nausea Vomiting Diarhoea	Anaphylaxis Dermatitis	Hypotension	
Others				
Day 2				Comments
DVT / TEE	Nausea Vomiting Diarhoea	Anaphylaxis Dermatitis	Hypotension	

Others				
Day 3				Comments
DVT / TEE	Nausea Vomiting Diarhoea	Anaphylaxis Dermatitis	Hypotension Dizziness	
Others				
Day 3-14				Comments
DVT / TEE	Nausea Vomiting Diarhoea	Anaphylaxis Dermatitis	Hypotension Dizziness	
Others				

**APPENDIX III: Transfusion Guidelines for patient's participating in
“EFFECTIVENESS OF PREOPERATIVE INTRAVENOUS TRANEXEMIC
ACID ON REDUCTION OF PERIOPERATIVE BLOOD LOSS IN OPEN
INTRAMEDULLARY NAIL FIXATION OF FEMORAL SHAFT FRACTURES
IN MULAGO” Study**

Category 1	Circle	Transfusion Criteria
Intraoperative Hemoglobin Concentration of < 7g/dl	YES / NO	Transfuse with 1 Unit of WB or PRBC if 1 Criteria in category 1 is met
Category 2		
Intraoperative Hemoglobin Concentration of < 10g/dl	YES / NO	Transfuse with 1 Unit of WB or PRBC if 1 criteria in Category 2 is met together with 3 criteria in Category 3
Category 3		
Severe bleeding at the surgical site and soiling of surgical drapes and mops	YES / NO	Transfuse with 1 Unit of WB or PRBC if ≥ 4 criteria in Category 3 are met
Tachycardia	YES / NO	
Oxygen Saturation < 90%	YES / NO	
Hypotension	YES / NO	
Severe pallor of the Mucous Membranes	YES / NO	
Decreasing Levels of Consciousness	YES / NO	
Dyspnoea	YES / NO	
Angina	YES / NO	

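### The safety outcome stops 72 hours after surgery, while follow-up and the data sheet run to day 14, so a late thromboembolic event is recorded but not part of the defined outcome

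*Combined protocol and SAP*

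**What the plan says.** The safety outcome is defined in one place only, section 3.8.2: "Will be described as adverse events secondary to administration of Tranexemic Acid observed in patients in the study during the perioperative period". Thromboembolic events are among the events listed beneath it. The Operational Definitions give the peri-operative period a fixed meaning: "Period from start of surgery to 72 hours after the Surgery". The abstract sets the same limit, saying that "adverse events in the peri operative period will be measured".

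Other parts of the plan go further in time. Section 3.7.7 states: "Patients shall be followed up for a period of 2 weeks post operatively". It also describes daily clinical review with "emphasis on identifying and addressing post-operative complications such as thromboembolic phenomena e.g. DVT". The data sheet in Appendix II has adverse event rows for the pre- and intraoperative period, Day 1, Day 2, Day 3 and Day 3-14. Each row has a DVT/TEE field.

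The analysis text for Objective 3 in section 3.12 is one sentence: "We will assess for safety using descriptive statistics showing proportions of adverse events in the study group". It gives no time window and no condition on cause. The safety objective in 1.6.2.2 gives no window either.

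**The concern.** Safety is part of the general objective and a named secondary objective, and thromboembolism is a listed safety event. Under section 3.2, DVT is not investigated routinely after surgery, though clinicians may do so at their discretion in patients at risk. Under 3.7.7, patients are worked up when features appear. An event is therefore usually dated when it is recognised, which may be after 72 hours. An outcome that closes at 72 hours leaves such an event out of the reported proportion even though the form holds it.

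Any error runs in one direction, towards apparent safety. Section 1.3 expects hospitals and the Ministry of Health to use the findings for guidelines. A thromboembolic rate of 0% that really means 0% by 72 hours could mislead those readers. Because 3.8.2 is restrictive and 3.12 is silent, the choice of event set could also be made after the data are seen, in an open-label study.

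Two further points are unclear rather than wrong.

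- **Start of the window.** The drug is given before skin incision. Section 3.7.4 measures surgical time from incision: "Time of skin incision and last skin suture will be documented to determine surgical time". If the start of surgery means incision, a reaction during the infusion falls outside the window, although the form has a row headed "Pre / Intraoperative Period".
- **Attribution.** Section 3.8.2 counts events that are secondary to the drug, and 3.12 has no such condition. No causality procedure or form field is described, so it is not clear who would make that judgement in an uncontrolled, open-label study.

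**Working it through.** The plan states no safety rate or safety sample size, so there is no figure to reproduce. The check sets the windows side by side and then sizes the effect of an omission.

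**1. The windows**

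| Place | Start | End | Condition on cause |
|---|---|---|---|
| Operational Definitions (peri-operative) | start of surgery | 72 hours | not applicable |
| 3.8.2, safety outcome | perioperative, so start of surgery | 72 hours | secondary to the drug |
| Abstract, Methods | perioperative | 72 hours | none |
| 3.7.7, follow-up | after surgery | 2 weeks | none |
| Appendix II, data sheet | pre/intraoperative | Day 14 | none |
| 3.12, Objective 3 | not stated | not stated | none |

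No section extends the outcome to day 14 or says how events in the Day 3-14 row are to be reported. In days, 72 hours is 3 of the 14 followed: 3/14 = 21% lie inside the outcome and 11/14 = 79% outside. That is a share of days, not of events.

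The rows Day 3 and Day 3-14 also overlap. A day 3 event could be entered twice, or placed on either side of the 72-hour cut.

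**2. Effect of one or two omitted events**

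Input: planned N = 43 (section 3.6). Intervals are exact (Clopper-Pearson). The lower limit solves P(X ≥ x) = 0.025 and the upper limit solves P(X ≤ x) = 0.025.

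- 1/43 = 2.33%, 95% CI 0.06% to 12.29%
- 2/43 = 4.65%, 95% CI 0.57% to 15.81%
- 0/43 = 0%, 95% CI 0% to 8.2%, where the upper limit is 1 − 0.025^(1/43) = 0.082

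One omitted event moves the result from the first line to the third. Two move it from the second line to the third.

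**3. Chance that an event is omitted**

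The documents give no thromboembolism rate and no timing. The values of p (14-day rate) and f (share of events after 72 hours) below are assumptions chosen only to show a range.

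P(at least one omitted) = 1 − (1 − p·f)^43

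| p | f = 25% | f = 50% | f = 75% |
|---|---|---|---|
| 1% | 10.2% | 19.4% | 27.7% |
| 2% | 19.4% | 35.1% | 47.8% |
| 5% | 41.8% | 66.3% | 80.7% |

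Expected omitted events are 43·p·f:

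- lowest corner: 43 × 0.01 × 0.25 = 0.11
- centre: 43 × 0.02 × 0.50 = 0.43
- highest corner: 43 × 0.05 × 0.75 = 1.61

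**The case against.** The strongest reply is that nothing in the plan says late events will be dropped. Section 3.12 has no time limit, the objectives have none, and the form carries the same DVT/TEE field through to day 14. On that reading the analyst tabulates everything on the form, and the 72-hour limit is only a loosely used word. This does not remove the problem. The term is formally defined, 72 hours is also when the blood loss measurement is taken, and 3.8.2 is the only text that says what the safety outcome is. What stands is that 3.12 leaves room to report late events. The plan therefore contradicts itself and does not consistently exclude them.

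Other points on that side have weight:

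- The range of 10% to 81% rests wholly on assumed inputs and is too wide to measure the bias.
- The intervals for 0/43 and 1/43 overlap heavily. With 43 patients and no control arm, neither supports a firm statement about thromboembolic safety.
- The outcome is secondary and descriptive. SAE reporting in 3.7.7 and DSMB review in 3.10 are not tied to the 72-hour definition.
- Section 3.7.7 does not say how patients are assessed after discharge. A Day 3-14 row shows that late events are meant to be collected, not that all of them will be found.

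These points limit the severity. They do not reconcile the sections.

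**Conclusion.** The concern holds. As written, the safety outcome ends 72 hours after surgery while follow-up and the form run to day 14, and 3.8.2 and 3.12 do not describe the same events. Confidence is high on that mismatch and moderate on the infusion and attribution points, which are ambiguities.

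The direction is certain given a fixed denominator: following 3.8.2 can only lower the reported thromboembolic proportion or leave it unchanged. The size is not known. One late event is worth 2.3 percentage points at N = 43. How likely such an omission is depends on a rate and a timing that the documents do not give.

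This should be corrected before analysis. It concerns what is reported and does not touch the primary outcome, SAE reporting or DSMB oversight.

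**What to change.** Define the safety outcome identically in 3.8.2 and 3.12, along these lines: all adverse events, whatever their attributed cause, from start of the tranexamic acid infusion to day 14. Tabulate them in three periods: infusion and intraoperative, then up to 72 hours, then after 72 hours to day 14. Report thromboembolic events separately, give each proportion an exact 95% CI, and treat any stated relationship to the drug as descriptive only.

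The essential part is the single window and the removal of the attribution condition. The tabulation and intervals make the result easier to read.

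Align the abstract. Add a note to the Operational Definitions that the safety window differs from the peri-operative period, which can stay as it is for blood loss and transfusion. Relabel the last row of the data sheet so that it no longer overlaps Day 3, for example as after 72 hours to Day 14.

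The cost is wording in three places, one note and one relabelled row. A relatedness field is needed only if relationship to the drug is to be described. No extra patients or tests are needed, and no extra visits provided the two-week follow-up is carried out as 3.7.7 states.

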3.1 Study design

This will be an open label single arm trial involving adult patients undergoing open intramedullary femoral shaft nail fixation at Mulago National Referral Hospital.

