3.7.6 Blood use in the perioperative period

The decision to transfuse patients in the intraoperative period will be taken by the anaesthesiologist in concert with the primary surgeon, Basing on:

- Visual assessment of the extent of soaking of the surgical mops with blood.
- Extent of pallor of the finger nail beds, palms and mucous membranes.
- Patient with features of severe hemodynamic instability, tachycardia, hypotension, dizziness etc.
- Post op hemoglobin results of severe anaemia ($\leq 6\text{g/dl}$)

The decision to transfuse patients in the postoperative period will be taken by the primary surgeon or the residents on the wards basing on:

- Patient with features of severe hemodynamic instability, tachycardia, hypotension, dizziness, palpitations etc.
- Extent of pallor of the finger nail beds, palms and mucous membranes.
- Post op hemoglobin results of severe anaemia ($\leq 6\text{g/dl}$)

Intraoperative and postoperative transfusion guidelines shall be availed to the teams to guide on when to transfuse patients to reduce on bias.

Whole blood and packed red blood cell units will be used. 450mls of whole blood and 200mls of packed red blood cells will be estimated to be equivalent to 1g/dl rise in hemoglobin level.

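### Section 3.8.2 limits the safety outcome to events attributed to tranexamic acid, while the rest of the plan counts adverse events without that limit; the narrower wording permits unblinded removal of events

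*Combined protocol and SAP*

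**What the plan says.** Safety is part of the general objective (section 1.6.1) and is the second secondary objective (section 1.6.2.2). Section 3.8.2 defines the outcome as follows: "Will be described as adverse events secondary to administration of Tranexemic Acid observed in patients in the study during the perioperative period". A list of event types comes next, including hypotension, dizziness and thromboembolic events.

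Other parts of the plan carry no causal condition:

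- Abstract: "adverse events in the peri operative period will be measured".
- Section 3.12, Objective 3: "We will assess for safety using descriptive statistics showing proportions of adverse events in the study group".
- Appendix II, procedure data: "7) Adverse Event/s Y N (Describe Event/s", followed by a by-period grid titled "Intraoperative and Post-operative Adverse Events and complications".
- Section 3.7.7: serious adverse events are reported within 24 hours, with no relatedness test.

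On design, section 3.1 states: "This will be an open label single arm trial involving adult patients".

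The operational definitions run the perioperative period from the start of surgery to 72 hours afterwards. Section 3.7.7 follows patients for two weeks, and the Appendix II grid runs from a pre/intraoperative block to a Day 3-14 block.

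**The concern.** Read plainly, section 3.8.2 counts an event only if someone judges that tranexamic acid caused it. Nothing in the plan supports that judgement. There is no concurrent group to show how often these events occur without the drug, everyone knows the treatment, and no criteria, assessor or adjudication step is given.

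The plan itself supplies other explanations for the listed events. Hypotension and dizziness appear in section 3.7.6 among the signs that prompt transfusion, both during surgery ("Patient with features of severe hemodynamic instability, tachycardia, hypotension, dizziness etc") and after it ("Patient with features of severe hemodynamic instability, tachycardia, hypotension, dizziness, palpitations etc"). Section 3.7.7 treats thromboembolism as a postoperative complication, and section 2.2 reports that its risk is no different with the drug. An investigator who accepts that background has a ready reason to call a thrombosis unrelated.

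Two analysts could therefore follow the plan faithfully, use the same forms and report different safety results. A reader of the results could not tell whether a low rate reflected what happened to patients or how events were attributed.

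**Working it through.** **Step 1. Compare the definitions.**

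| Place | Causal condition? | Period covered |
|---|---|---|
| Abstract | No | Perioperative |
| 3.8.2 | Yes | Perioperative (start of surgery to 72 h) |
| 3.12, Objective 3 | No | Not stated |
| Appendix II form | No; no relatedness field | Pre/intraoperative to Day 14 |
| 3.7.7, serious events | No | Follow-up of 2 weeks |

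Only 3.8.2 is restricted by cause. The periods also differ. Section 3.7.3 gives the drug before skin incision, so a reaction during the infusion precedes the start of surgery and falls outside the literal 3.8.2 window. So does a thrombosis found after 72 hours. The form has blocks for both.

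**Step 2. Denominator.** The plan gives no figure for the safety outcome, so its sample size is used only as a denominator. From section 3.6.1:

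n = 2 × 1.56² × (1.96 + 0.84)² / 0.993² = 38.70, rounded to 39

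39 / 0.9 = 43.3, which the plan takes as 43. Both figures reproduce, apart from rounding the last one down instead of up to 44, which does not matter here.

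**Step 3. Effect of each attribution ruling.** For a given set of recorded events, counting a subset cannot raise the number. Each patient removed changes the proportion by 1/43 = 2.3 percentage points. The documents give no expected event rate, so the counts below are assumptions. Intervals are exact (Clopper-Pearson), two-sided 95%; with no events the upper limit is 1 − 0.025^(1/43) = 8.2%.

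| Patients counted, of 43 | Proportion | 95% CI |
|---|---|---|
| 9 | 20.9% | 10.0% to 36.0% |
| 7 | 16.3% | 6.8% to 30.7% |
| 4 | 9.3% | 2.6% to 22.1% |
| 2 | 4.7% | 0.6% to 15.8% |
| 0 | 0% | 0% to 8.2% |

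If nine patients had a listed event, the reported figure could fall anywhere from 20.9% to 0%, depending only on attribution. If two patients had a thrombosis and both were put down to the fracture, 4.7% would become 0%.

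**Step 4. Chance of reporting no events.** Let p be the true all-cause rate and q the chance that an event is attributed to the drug, both assumed. The chance of a zero count is (1 − pq)^43.

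| p | q = 1 (all counted) | q = 0.5 | q = 0.25 |
|---|---|---|---|
| 2% | 42% | 65% | 81% |
| 5% | 11% | 34% | 58% |
| 10% | 1% | 11% | 34% |

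For example, at p = 5% and q = 0.5: (1 − 0.025)^43 = 0.34.

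**The case against.** The strongest reply is that one phrase carries the whole point. Every other safety passage is unrestricted, including section 3.12, which sets what is tabulated. The plan contains no attribution step, so no planned mechanism removes an event. The phrase may simply be a loose introduction to a list of expected effects that largely matches those in section 2.2. There are also safeguards. Serious events go to the department, the ethics committee and the drug authority whatever their cause. An independent monitoring board reviews safety (sections 3.10.1 to 3.10.3), and suspected thromboembolism is investigated with coagulation tests and Doppler studies. Finally, the example counts are invented.

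Much of this stands. A reader might infer that the trial plans to count only drug-caused events, or that harms will be hidden. The documents do not support either inference: filtering is allowed by one inconsistent definition, and the raw events should still be on the forms. The figures above show sensitivity and are not predictions.

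The reply does not remove the defect. Section 3.8.2 is the place where the outcome is defined, and the safeguards do not fix which events enter its numerator. The missing causality field does not settle the matter either, since free-text and comment spaces could carry an unplanned ruling. If all events were always intended, correcting the wording loses nothing.

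**Conclusion.** The point holds as an inconsistency with a one-directional risk. Section 3.8.2 restricts safety by judged cause, the rest of the plan does not, and the design gives no basis for the judgement. Applying 3.8.2 literally can lower the reported rate by 2.3 percentage points per patient reclassified and can never raise it. The total effect cannot be estimated, because the documents give neither an event rate nor an attribution rate. The mismatch in wording is certain; the bias is possible. It should be corrected before the data are analysed.

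A reader might also infer that counting all events would show whether tranexamic acid is safe. It would not. With one arm, hypotension from bleeding is counted along with any hypotension from the drug, so the proportions describe what happened to patients and cannot be assigned to the treatment.

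**What to change.** 1. In section 3.8.2, define safety as all adverse events regardless of judged cause, matching section 3.12.
2. In section 3.12, report the number and proportion of patients with each listed event, with exact 95% confidence intervals, counting each patient once per event type.
3. State one observation window that includes the tranexamic acid infusion. Reconcile the 72-hour perioperative definition with the two-week follow-up and the form's Day 3-14 block. Removing only the causal phrase would leave the window unresolved.
4. If relatedness is wanted, add a field with stated criteria and a named assessor role, and report it only as a supplementary column.
5. Check that the Appendix II grid names dizziness in every block. In the text as extracted it appears only from Day 3, which may be an artefact; if it is not, earlier dizziness depends on the space for other events.

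The cost is a few lines of wording and possibly a small form edit, with no new visits, tests or patients. The reported proportions may be higher, and the report should say that without a comparator they do not show that tranexamic acid caused the events.
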